# D. The data collection and measurement techniques are appropriate and effective

# Experimental Design

The overall research design is a within-group, randomized controlled study to compare analgesic effects between EStim and BreEStim (single-session in Exp 1, long-term intervention in Exp 3), between BreEStim120 and BreEStim240 (Exp2). We prefer this within-group comparison because 1) pain, by nature, is a subjective perception, it is difficult to control (physical, social, psychological) multi-factors between two groups; 2) It will be fair that all subjects receive the innovative intervention, which is superior to regular electrical stimulation according to our pilot data; 3) according to our recent BreEStim study in patients with spinal cord injury, the duration of analgesic effect was 15 hours after one-session of BreEStim treatment. An interval of one week for washout should be sufficient for Exp 1 & 2. The washout interval will be 2 weeks for Exp 3. It is our experience with subjects with spinal cord injury that an interval of 7 days is sufficient for subjects to return to their baseline after BreEStim treatment. (Li et al. 2016; Karri et al. 2018b; Li et al. 2018) However, we did notice that one subject with post-amputation PLP had carry-over effect for one month(Li et al. 2012a). We plan to screen these patients with longlasting carry-over effects. These patients will be excluded from the subject should this happen.

In Experiment 1, we plan to use our recent BreEStim and EStim protocols (Li et al. 2013; Li et al. 2014; Li et al. 2016) to measure mechanical sensation threshold, thermal (cold/warm detection, cold/hot pain) thresholds, and electrical sensation and pain thresholds in the treatment limb and contralateral limb. The same group of subjects will receive both BreEStim and EStim at a randomized yet balanced order with at least 7 days apart. The same amount of electrical stimulation (120 stimuli) will be given during both BreEStim and EStim. The purpose of this aim is to investigate whether BreEStim could have better analgesic effect than EStim in amputee subjects with chronic phantom limb pain as we observed in healthy subjects. We expect increased electrical pain thresholds in both limbs after BreEStim because of its central desensitization effects.

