In Experiment 2, a group of subjects will receive BreEStim at two different doses (120 vs. 240 stimuli) on two different days with at least 7 days apart. The purpose is to compare the extent and duration of analysesic effects between two doses of BreEStim. We expect that BreEStim240 could have similar degree of pain reduction but with longer duration compared to BreEStim120, as shown in our pilot study. Therefore, we expect to use BreEStim240 in Experiment 3 for the long-term intervention.

[figure not shown]

Figure 7: Illustration of study design for Experiments 3

The University of Texas

IRB NUMBER: HSC-MS-20-1032 UTHealth IRB APPROVAL DATE: 12/03/2020

In Experiment 3, the same established protocol will be used (Li et al. 2012a; Li 2013). The effect of two interventions (BreEStim and EStim) will be compared. Each intervention consists of 240 stimuli/session (about 40-50 min/session), 1 session/day for 10 consecutive sessions (over 2 weeks). After a follow-up (wash-out) period of two weeks, the same subject will be treated with the other intervention with a same follow up of 2 weeks. The intensity of stimulation will be adjusted as subjects could tolerate. Electrical stimulation will be delivered to the median nerve on the dominant side. The wash-out/follow-up period of 2 weeks allows removal of accumulative or carry-over effect from the previous intervention.

It is expected that electrical pain threshold will be further increased after BreEStim with parallel reduction in pain perception, while there is no or minimum change after EStim and no significant change in pain perception. Pain threshold will be measured using QST. Pain perception will be characterized by duration and amount of change in pain on visual analog scale (VAS), i.e., how much pain is reduced and how long it lasts. As such the effect of treatment is quantified by reduction x hours.

The secondary outcome measurement will be General Well-Being (GWB) Schedule Survey and Center for Epidemiologic Studies Depression Scale (CES-D), NIMH Survey to examine the possible effect of pain reduction on general well-being, depression and quality of life of the patients. These surveys have been well validated and commonly used (Sherman et al. 1984; Wartan et al. 1997; Kooijman et al. 2000).

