### 5. Human Subjects

As mentioned above, we plan to recruit a total of 64 amputee subjects with phantom limb pain, including 16 subjects for Aim 1, 18 subjects for Aim 2, and 30 subjects for Aim 3. The number of subjects was estimated based on the pilot data.

Subject recruitment/assignment

IRB NUMBER: HSC-MS-20-1032 UTHealth IRB APPROVAL DATE: 12/03/2020

The collaborating physician (Co-I, [name]) will screen patients from the outpatient clinic of TIRR Memorial Hermann Hospital. We plan to register the project on www.clinicaltrials.gov. If patients are not currently seen by [name], but are willing to participate in the project, they need to see [name] for screening and monitoring. In addition, [name] will monitor medical conditions of the patients and manage medical problems as needed. Patients will be recruited and enrolled in the project if they meet the following criteria:

Inclusion criteria: A patient who 1) has neuropathic PLP after amputation of one limb, upper or lower limb; NOTE that BreEStim has been shown to be effective for neuropathic pain management in patients after traumatic and non-traumatic spinal cord injury in recent studies(Li et al. 2016; Li et al. 2018). Therefore, we plan to recruit patients with chronic neuropathic PLP from both traumatic and non-traumatic limb amputation. 2) has chronic pain, >3 months; 3) is between 18 to 75 years of age; 4) is stable on oral pain medications at least two weeks. Patients are instructed to continue their pain medications as prescribed during the intervention period.

**Exclusion criteria:** Patients will be excluded if they 1) are currently adjusting oral pain medications for their neuropathic pain; 2) have pain, but not neuropathic, e.g., from inflammation at the incision wound of the residual limb; 3) have a pacemaker to avoid possible side effect of electrical stimulation; 4) have amputation in multiple limbs; 5) are not able to follow commands, or to give consent; 6) have asthma or other pulmonary disease; 7) are not medically stable.

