# 6. Data Collection and Analysis

Data collection details have been described above. Data analysis is described here.

**Experiment 1** Repeated-measures two-way ANOVA tests with factors INTERVENTION (2 levels, BreEStim and EStim) and TIME (pre- and post-intervention) will be tested on dependent variables, including VAS, QST thresholds (tactile, electrical, and thermal), to determine statistical significance between two interventions. Paired t-tests will be used to compare the duration of lasting hours between two interventions. p value is set at 0.05. As observed in the pilot data, we expect that BreEStim could have central desensitization and analgesic effects on patients with phantom limb pain, but no such effect after EStim. These findings would suggest that the central desensitization effect of BreEStim could be translated to analgesic effects in patients with PLP. Furthermore, the findings of analgesic effects along with desensitization effects in patients with PLP support central sensitization as a plausible mechanism that mediates post-traumatic PLP.

Experiment 2 Similar to Exp 1, repeated-measures two-way ANOVA tests with factors INTERVENTION (2 levels, BreEStim 120 vs. 240) and TIME (pre- and post-intervention) will be tested on dependent variables, including VAS, QST thresholds (tactile, electrical, and thermal), to determine statistical significance between two interventions. Paired t-tests will be used to compare the duration of analgesic effect (lasting hours) between two interventions. p value is set at 0.05. As shown in the pilot data, we expect that BreEStim could have dose-dependent effects on the duration but not the degree of analgesic effects. These results also suggest that BreEStim could have cumulative effects if patients receive interventions repeatedly over a period of time.

In Experiment 3, Repeated-measures two-way ANOVA will be performed to determine statistical significance between two interventions. Factors include INTERVENTION (BreEStim vs. EStim) and TREATMENT (Pre- and Post-intervention, and Followup). Variables are VAS and modified VAS and QST parameters, GWB, and CES-D. It is hypothesized that the effect of pain reduction is greater in BreEStim than in EStim for amputation patients, manifested by pain reduction on VAS assessment and parallel change of increased electrical pain threshold as shown by pilot data in Experiments 3. Furthermore, pain reduction is accompanied by improvement in general well-being and mood.

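### Experiment 3 collects GWB and CES-D to examine the effect of pain reduction on well-being and mood, but no term in the planned ANOVA relates pain change to either questionnaire

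*Combined protocol and SAP*

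**What the plan says.** The Experimental Design section introduces the General Well-Being Schedule (GWB) and the CES-D depression scale as the secondary outcomes of Experiment 3. It gives their purpose as "to examine the possible effect of pain reduction on general well-being, depression and quality of life of the patients". Section 6 closes the Experiment 3 paragraph with the matching hypothesis: "Furthermore, pain reduction is accompanied by improvement in general well-being and mood".

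The analysis is set out in three sentences of Section 6:

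- The method and its purpose: "In Experiment 3, Repeated-measures two-way ANOVA will be performed to determine statistical significance between two interventions"
- The terms in the model: "Factors include INTERVENTION (BreEStim vs. EStim) and TREATMENT (Pre- and Post-intervention, and Followup", that is, two interventions by three time points
- The outcomes to which it is applied: "Variables are VAS and modified VAS and QST parameters, GWB, and CES-D"

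VAS, GWB and CES-D therefore each appear as an outcome. The analysis section contains no correlation, regression, covariate or mediation analysis that joins them.

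Specific Aim 3 is worded differently. It says that the effect on general well-being will be assessed, and in context this is the effect of the treatment. The experiment is a crossover with "30 subjects for Aim 3".

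**The concern.** In the Experimental Design sentence, pain reduction is the explanatory variable and well-being and depression are the responses. The matching null is that a patient's pain change is unrelated to that patient's change in GWB or CES-D. The ANOVA has other nulls: that the questionnaire profile is the same under both interventions, or that it does not change over time. Neither involves pain.

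Two errors of inference become possible.

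- **A difference that does not come through pain.** GWB may be better under BreEStim for another reason. Section 3 offers one: it presents BreEStim as patient-centred and suggests that active participation may help psychological function. A significant interaction would then say nothing about pain relief.
- **A link that the interaction cannot show.** Well-being may follow pain relief closely from patient to patient. If the two interventions relieve pain to a similar degree, there is little mean GWB difference for the interaction to find.

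**Working it through.** **Inputs from the documents.** Experiment 3 has 30 subjects, each receiving both interventions. Section 6 says "p value is set at 0.05" for Experiments 1 and 2; I assume the same level, two-sided, for Experiment 3. The large effect size of 0.8 used to plan Experiments 1 and 2 serves as a benchmark.

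**Inputs assumed.** The documents give no SD for GWB or CES-D and no correlation between pain and well-being. Every rate below is therefore conditional and shown over a range.

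**No planned figure to reproduce.** The text available to me gives no power for GWB, CES-D or their link with pain, and does not include the derivation of the 30.

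**Model.** For each patient, let v be the BreEStim-minus-EStim difference in pain relief and g the same difference in GWB improvement, each scaled to SD 1. Let D be the mean of v, r the correlation of g with v, and b an intervention effect on GWB that does not pass through pain. Then g = b + r·v + error, and the mean of g is b + r·D.

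**The two tests**

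- ANOVA interaction, post-minus-pre contrast: a one-sample t-test on g. Its power comes from the noncentral t with 29 degrees of freedom and noncentrality (b + r·D)·√30.
- Association: t = r̂·√(28/(1 − r̂²)) with 28 degrees of freedom, where r̂ is the sample correlation; power by simulation.

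**Case 1: no link (r = 0), GWB advantage from other causes**

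| b (SD) | Noncentrality | ANOVA contrast rejects | Association test rejects |
|---|---|---|---|
| 0.3 | 0.3 × √30 = 1.64 | 36% | 5% |
| 0.5 | 0.5 × √30 = 2.74 | 75% | 5% |

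Using all three time points, the interaction F-test at b = 0.5 rejects 65% to 80% of the time, depending on how much of the effect lasts to follow-up.

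**Case 2: real link (r = 0.5), no other effect (b = 0)**

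| D (SD) | r·D | ANOVA contrast power | Association test power |
|---|---|---|---|
| 0 | 0 | 5% | 83% |
| 0.6 | 0.30 | 36% | 83% |
| 0.8 | 0.40 | 56% | 83% |
| 1.0 | 0.50 | 75% | 83% |

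At D = 0.8 the three-time-point F-test has 47% to 59% power. At D = 0.8 with r = 0.7, the two-time contrast has 84%. Its power falls below 50% only when r·D is below 0.37 SD, and it reaches 80% at 0.53 SD.

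**Limits of the association test.** At r = 0.3 its power is only about 37%. With 27 completers (the 10% withdrawal stated for Experiment 1, applied here as an assumption: 30 × 0.9 = 27), it is about 33% at r = 0.3 and 79% at r = 0.5.

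**The case against.** **The ANOVA answers a question the protocol does ask.** Specific Aim 3 speaks of the effect on well-being, which the intervention-by-time interaction tests. The Section 6 hypothesis can also mean parallel mean improvement, with VAS falling and GWB improving under the same intervention. The sentence before it describes pain and pain threshold in that way, and separate ANOVAs serve that reading. This stands. The mismatch rests mainly on the Experimental Design sentence, which is itself worded as a possible effect on secondary outcomes.

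**The ANOVA does more than compare interventions.** A reader might infer that it tests nothing else. The time factor also tests average change across both interventions, so if both relieve pain and well-being follows, the plan may show an improvement over time. That is correct, but this term contains no pain change either.

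**The power comparison is not like for like.** The two tests have different nulls, and the figures rest on chosen inputs. This stands. The figures show how far the two questions can diverge; they are not a predicted power loss.

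**The regression has its own weaknesses.** A slope can be significant when BreEStim gives no extra pain relief and no extra well-being (D = 0 above). Expectation could also move both self-reports. If a shared cause explained 30% to 50% of the variance of each, with no path from pain to GWB, the correlation would be 0.3 to 0.5. The association test would then reject about 37% to 83% of the time. This stands and limits what the slope can support.

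**Conclusion.** The mismatch is real and follows from the text alone: the question about the effect of pain reduction on well-being and depression has no analysis that uses pain change. A significant GWB or CES-D interaction would not show that well-being follows pain relief, and a non-significant one would not show that it does not.

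The size is conditional. With no link, the contrast rejects 36% to 75% of the time under a direct GWB effect of 0.3 to 0.5 SD. With r = 0.5, its power runs from 5% to 75% as the pain difference goes from 0 to 1.0 SD. These figures assume 30 complete patients, two-sided 5% and the unit-SD model above.

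Two stronger readings are not supported.

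- A reader might infer that the ANOVA usually misses a real link. That depends on the between-intervention pain difference and the strength of the link: at the 0.8 benchmark, power is 56% with r = 0.5 and 84% with r = 0.7.
- A reader might infer that the plan commits the sponsor to a wrong conclusion. The documents state no rule for interpreting either a significant or a non-significant questionnaire result.

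The point is worth acting on, but it concerns secondary outcomes.

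**What to change.** Keep the ANOVAs on VAS, GWB and CES-D, and draw only intervention and time conclusions from them.

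Add to Section 6, before data are examined, a within-patient regression for each questionnaire:

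- **Response:** the patient's BreEStim-minus-EStim difference in GWB change (and, separately, in CES-D change).
- **Explanatory variable:** the same patient's difference in VAS change over the same named time points.
- **Adjustment:** treatment sequence, which removes a period effect from the within-patient differences.
- **Report:** the slope with its 95% confidence interval.

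State that the slope is read together with the ANOVA results for VAS and the questionnaire, and that it is an association which does not exclude shared causes such as expectation.

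If the sponsor does not want this analysis, the alternative is to reword the purpose in Experimental Design and the hypothesis in Section 6 so that they claim only a between-intervention difference in well-being and mood.

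The cost is a few sentences and one exploratory regression per questionnaire on data already planned. The slope comes from about 30 patients and will be imprecise if the link is weak.

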#### 7. Potential Risks/Discomforts:

The risks associated with this study are minimal. Electrical stimulation has been used extensively in clinical settings. Patients may feel uncomfortable, or even painful during electrical stimulation. The patients will be specifically instructed that they are encouraged to increase the intensity of electrical stimulation to the level they may feel comfortable, but they need to be able to tolerate at that level if given repetitively. They are also explicitly instructed to decrease the intensity of electrical stimulation if they can not tolerate it. Surface electrodes can cause skin irritation from the tape adhesive or the electrode paste. Breathing through a face mask may be make patients feel uncomfortable. All tested subjects in the previous studies (approximately 100 subjects, including patients) tolerated the mask well.

### 8. Benefits:

There are several potential benefits in this study: 1) direct benefit to subjects as their neuropathic pain may be relieved by the intervention; 2) benefit to the class of subjects: other patients in the same patient population may be benefit if the intervention is applied to them; 3) adding to the knowledge base: the findings will be definitely added to the knowledge base. Specifically, the study will provide evidence of an alternative and innovative intervention for neuropathic pain management after amputation.

#### 9. Risk-benefit Ratio:

In view of the minimal risk, the knowledge to be gained far outweighs the risks.

#### 10. Consent Procedures:

Informed consent will be obtained from the subject. After the subject is identified and is interested in participating, informed, written consent will be obtained by the investigator.

# 11. Confidentiality Procedures:

In order to minimize risk to confidentiality, all data will be de-identified, coded with a study-specific identification number, maintained on a password-protected server, and/or kept in a locked office. No findings will be released without written authorization by the subject or requests by law.

## 12. Costs:

The subject will not be expected to pay any costs.

### 13. Payments:

Subjects will receive a gift card of \$40 for their participation in each session for Experiment 1 and 2. Experiment 3, each subject will have a total of 20 sessions (10 consecutive sessions of BreEStim, and 10 consecutive sessions of EStim, with 2 weeks apart). Each subject will receive a giftcare of \$40 after the first session. Each of them will receive a total of \$800 after the completion of all 20 sessions. No monetary compensation will be given if 20 sessions are not completed. This is to keep commitment and for subject retention.

